6.20.4.1.2. Extra-nodal Index Lesions

An extra-nodal mass may be selected as an index lesion if it is both abnormal and measurable at baseline. An extra-nodal mass of any size is considered abnormal. It is considered measurable if it has 2 perpendicular diameters that can be accurately measured in cross section with the LD being ≥ 1.0 cm and the LPD also being ≥ 1.0 cm.

6.20.4.2. Non-Index Lesions

Any other measurable and abnormal nodal or extra-nodal lesions not selected for quantitation as index lesions may be considered non-index lesions. In addition, non-measurable evidence of lymphoma such as nodal lesions or extra-nodal lesions with both diameters < 1.0 cm, bone lesions, leptomeningeal disease, ascites, pleural or pericardial effusions, lymphangitis of the skin or lung, abdominal masses that are not confirmed and followed by imaging techniques, cystic lesions, or lesions with artifacts may be considered as non-index disease.

The presence or absence of non-index disease should be recorded at baseline and at the stipulated intervals during treatment. If present at baseline, up to 6 non-index lesions should be recorded. The non-index disease at baseline will be used as a general reference to further characterize regression or progression of lymphoma during assessments of the objective tumor response during treatment. Measurements are not required and these lesions should be followed as “present”, “unequivocally progressed” or “absent”.

6.20.5. Follow-up of Index and Non-Index Tumor Lesions

6.20.5.1. Nodal Lesions

At follow-up time points, the LDs for individual nodal lesions and the SPD of all nodal index lesions will be considered. Because nodal index lesions that have one or both diameters > 0 cm and < 1.0 cm cannot be reliably measured, a default value of 1.0 cm will be assigned for each diameter that meets these criteria and the resulting PPD will be used in SPD calculations. Based on this convention, a CR may be achieved even if an SPD value is > 0 cm².

New or enlarging nodal lesions that are still ≤ 1.0 cm by ≤ 1.0 cm will not be considered to represent recurrent or progressive disease. A new node that measures > 1.5 cm in any diameter or a new node that measures > 1.0 cm to ≤ 1.5 cm in the LD and measures > 1.0 cm in the LPD will be considered progressive disease.

In cases in which a large lymph node mass has split into multiple components, all subcomponents regardless of size will be used in calculating the SPD. Progression will be based on the SPD of all sub-components. Lesion sub-components will have PPDs calculated. Similarly, lesion sub-components that are visible but neither abnormal nor measurable will have the default PPD of 1.0 cm² (1.0 cm × 1.0 cm) used in calculating the SPD.

If lesions merge, a boundary between the lesions will be established so the LD of each individual lesion can continue to be measured. If the lesions have merged in a way that they can no longer be separated by this boundary, the newly merged lesion will be measured bi-dimensionally.

6.20.5.2. Extra-nodal Lesions

At follow-up time points, the LD of each single extra-nodal lesion and the SPD of all extra-nodal index lesions will be considered. Because extra-nodal index lesions that have one or both diameters < 1.0 cm and > 0 cm cannot be reliably measured, a default value of 1.0 cm will be assigned for each diameter that meets these criteria and the resulting PPD will be used in SPD calculations. If an extra-nodal lesion is no longer clearly visible, it will be considered resolved and its PPD will be defined as 0 cm².

If an extra-nodal lesion that had resolved (ie, had a PPD of 0 cm²) subsequently reappears unequivocally, the subject will be considered to have progressive disease. A new unequivocal extra-nodal lesion of any size that appears at a site that was not previously involved with lymphoma and is discernable to the radiologist by CT/MRI scan will be considered progressive disease.

6.20.5.3. Definition of Diffuse Disease in the Liver and Spleen

The radiologist will make a qualitative assessment of change in the size of the liver and spleen, and will not perform quantitative measurements of these organs.

Liver and spleen size should be reported as normal, enlarged not due to lymphoma, enlarged due to lymphoma (nodules must be present for this to be reported), unequivocal increase not due to lymphoma, or unequivocal progression (nodules must be present for this to be reported).

6.20.5.4. Bone Marrow

Bone marrow assessments will be based on morphologic evaluation of bone marrow biopsies. Immunohistochemistry may be used to assess response if the sample is indeterminate by morphology.

In a subject who has a baseline bone marrow biopsy showing bone marrow NHL or does not have a baseline bone marrow examination, declaration of an on-study CR requires bone marrow biopsy documentation of the absence of bone marrow NHL. In a subject who has a baseline bone marrow biopsy showing no evidence of NHL, declaration of an on-study CR does not require bone marrow examination as long as other criteria for CR are met.

6.20.5.5. Biopsy

Biopsy is not required in the determination of subject eligibility. However, subjects with evidence of transformed aggressive lymphoma on biopsy are ineligible for study participation.

During study participation, a subject who has a biopsy indicating transformation to an aggressive lymphoma will be considered to have PD even in the absence of other evidence of PD. If the subject has no earlier objective documentation of PD, the date of the biopsy will be considered the date of NHL progression.

6.20.5.6. Serum Monoclonal IgM Protein (LPL/WM Only)

Assessment of circulating monoclonal IgM by quantitative SPEP and IFE should be performed for subjects with LPL/WM.

6.20.6. Date of Time Point Response and Progression

For subjects who have imaging examinations on various dates that are nevertheless assigned to the same time point, the following rules apply for the calculation of the endpoint date:

- The response date will be the last date associated with that particular imaging time point.
- The progression date will be the first date associated with that particular imaging time point.

6.20.7. Definitions of Tumor Response and Progression

6.20.7.1. Best Overall Response

Responses will be categorized as CR, PR, SD, or PD. In addition, a response category of not evaluable (NE) is provided for situations in which there is inadequate information to otherwise categorize response status. A response category of no disease (ND) is included for situations in which there is no evidence of tumor either at baseline or on treatment.

The best overall response will be determined. The best overall response is the best response recorded from the start of treatment until progressive disease/recurrence (taking as reference for PD the smallest measurements recorded since treatment started). Subjects with NE or ND will be counted as failures in the analyses of tumor response.

- A radiological best overall response of CR, PR, SD, PD, NE and ND is allowed.
- Neither a PR nor an SD designation may follow a CR. Once a CR is observed, the subject will continue to be considered to have CR status until the criteria for PD are met.
- An SD designation may not follow a PR designation. In cases where a subject has an apparent worsening of lesions following a PR, the subject will continue to be considered to have PR status until the criteria for PD are met.

- Subjects will be defined NE if there is no adequate on-treatment radiological response assessment. NOTE: These subjects will be counted as failures in the primary analysis of tumor response data.
- For subjects with LPL/WM, a minor response and very good partial response is allowed based on a reduction of monoclonal IgM concentrations.

6.20.7.2. Complete Response

To satisfy criteria for a CR, all of the following criteria must be met:

- No evidence of new disease
- Regression of all index nodal masses to normal size (ie, \leq 1.5 cm in the LD for nodes that were considered large at baseline and \leq 1.0 cm in the LD for nodes that were considered small at baseline) (see Section 6.20.4.1.1 for definitions of large and small nodes)
- Regression to normal of all nodal non-index disease and disappearance of all detectable extra-nodal index and non-index disease
- Normal spleen and liver size by imaging studies, no hepatic or splenic lymphoma nodules, and no new organ enlargement
- Morphologically negative bone marrow based on an adequate unilateral core biopsy (> 20 mm unilateral core); if the sample is indeterminate by morphology, it should be negative by immunohistochemistry
- If PET performed (eg, for DLBCL), no evidence of residual disease
- If the subject has WM, disappearance of serum monoclonal protein by IFE and normal serum IgM level

6.20.7.3. Very Good Partial Response (LPL/WM) only

To satisfy criteria for VGPR, both of the following criteria must be met:

- A $>90\%$ decrease from baseline in monoclonal IgM concentration by SPEP or total serum IgM quantitation by nephelometry
- Other criteria for CR are met (see Section 6.20.7.2)

6.20.7.4. Partial Response

To satisfy criteria for a PR, all of the following criteria must be met except for subjects with WM as noted below:

- No evidence of new disease
- A $\geq 50\%$ decrease from baseline in the SPD of the index nodal and extra-nodal lesions (eg, splenic or hepatic nodules)

- No increase in the size of non-index nodes or non-measurable disease
- No increase in the size of the liver or spleen and no new organ enlargement
- Persistence of bone marrow involvement in a subject who meets other criteria for CR based on the disappearance all nodal and extra-nodal masses
- If PET performed (eg, for DLBCL):
 - Typically FDG-avid lymphoma: if no pretreatment MRI
 - scan or if the PET scan was positive before therapy, the on-treatment PET is positive in ≥ 1 previously involved site
 - Variably FDG-avid lymphoma/FDG-avidity unknown: if no pretreatment PET scan or if the pretreatment PET scan was negative for lymphoma, CT criteria should be used in assessing the tumor during treatment. If the PET scan was positive before therapy, the on-treatment PET is positive in ≥ 1 previously involved site.
- For subjects with LPL/WM:
 - A $\geq 50\%$ decrease from baseline in monoclonal IgM concentration by SPEP or total serum IgM quantitation by nephelometry
 - Any decrease from baseline in the SPD of the index nodal and extra-nodal lesions (eg, splenic or hepatic nodules)

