- c) The previously BCR treated patients will be limited to subjects with CLL (other BCR targeted therapies may be accepted after approval of the medical monitor) only in the context of this cohort are Richter's transformation eligible.
 - i) CLL subjects whom have had more than 1 BCR targeted therapy will be enrolled into the cohort of the most recent treatment ibrutinib or idelalisib received prior to progression.

- 5) Presence of radiographically measurable progressive disease as defined using Cheson criteria for NHL, and iNHL and by IWCLL criteria for CLL; lymphadenopathy or extranodal lymphoid malignancy (defined as the presence of ≥ 1 lesion that measures ≥ 2.0 cm in the longest diameter [LD] and ≥ 1.0 cm in the longest perpendicular diameter [LPD] as assessed by CT or MRI);
 - a) Subjects with LPL/WM who do not have radiographically measurable progressive disease must have a monoclonal serum IgM $\geq 2x$ ULN as verified by serum protein electrophoresis (SPEP) and with lymphoplasmacytic marrow involvement are eligible. LPL/WM enrollment is limited to those sites which have cryoglobulin analysis capabilities
- 6) All acute toxic effects of any prior antitumor therapy resolved to Grade ≤ 1 before the start of study drug (with the exception of alopecia [Grade 1 or 2 permitted], neurotoxicity [Grade 1 or 2 permitted], or bone marrow parameters [Grade 1, 2, or 3 permitted])
- 7) Karnofsky performance status of ≥ 60
- 8) Life expectancy of at least 3 months
- 9) Required screening laboratory data (within 5 weeks prior to administration of study drug) as shown in **Table 4-1**. *Note: Confirmation should be considered for out-of-range values to determine if the abnormality is real or artifactual. Values used for screening must be obtained within the screening period and should be the most recent measurement obtained. Subjects with any degree of neutropenia, thrombocytopenia, or anemia with documentation that it is due to malignancy may enroll.*

Table 4-1. Required Screening Laboratory Values

Organ System	Parameter	Required Value
Hematopoietic	ANC	$\geq 0.5 \times 10^9/L$
	Platelets	$\geq 50 \times 10^9/L$
	Hemoglobin	$\geq 80 \text{ g/L (8.0 g/dL)}$
Hepatic	Serum total bilirubin	$\leq 1.5 \times \text{ULN}$ (unless elevated due to Gilbert's syndrome or hemolysis)
	Serum ALT	$\leq 2.5 \times \text{ULN}$
	Serum AST	

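### Applied literally, the NHL response criteria deny responder status to LPL/WM subjects with a deep IgM fall but no SPD decrease, and to shrinking tumours whose PET turns negative, so ORR may be understated

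*Protocol*

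**What the plan says.** The NHL categories are defined in Protocol 6.20.7.

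- **PR (6.20.7.4).** The list opens with "all of the following criteria must be met except for subjects with WM as noted below". Its items include an SPD decrease of at least 50%; a marrow item, "Persistence of bone marrow involvement in a subject who meets other criteria for CR" through loss of all masses; and, where PET was done, the clause "if the PET scan was positive before therapy, the on-treatment PET is positive in" at least one previously involved site. For LPL/WM it asks for an IgM fall of at least 50% and "Any decrease from baseline in the SPD of the index nodal and extra-nodal lesions".
- **CR (6.20.7.2).** Index nodes must be back to normal by measurement and the marrow must be negative. On PET: "If PET performed (eg, for DLBCL), no evidence of residual disease". In WM the monoclonal protein must also be gone and IgM normal.
- **VGPR (6.20.7.3).** An IgM fall above 90%, and "Other criteria for CR are met".
- **MR (6.20.7.5).** An IgM fall from 25% to below 50%, with no SPD increase.
- **SD (6.20.7.6).** For LPL/WM, the IgM fall must be too small for MR or PR.

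Eligibility criterion 5a (Protocol 4.2.1) admits node-free disease: "Subjects with LPL/WM who do not have radiographically measurable progressive disease must have a monoclonal serum IgM" of at least twice the upper limit of normal, with marrow involvement. Protocol 6.5 waives repeat scans for LPL/WM subjects with no adenopathy at screening, unless clinically indicated. PET is optional (6.20.2) and is not in the procedures table.

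SAP 6.1.1 takes NHL response from Protocol 6.20. SAP 6.2.1 counts CR and PR (plus VGPR and MR in LPL/WM) in ORR, as read by the independent review committee (IRC). SAP 6.2.2.2 and 6.2.2.3 restrict DOR and TTR to responders. SAP 6.3 drops the sensitivity analyses.

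**The concern.** A response scale should be monotone: a better result should never cost a subject responder status. Two parts of 6.20.7 break that rule. In LPL/WM, the MR ceiling and the PR requirement for an SPD decrease leave a hole above a 50% IgM fall for anyone whose SPD cannot or does not decrease, and the protocol deliberately enrols such subjects. In PET-assessed disease, a PET that turns negative fails the PR clause, while a node still enlarged by measurement blocks CR.

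ORR is a secondary endpoint, and responder status also selects the subjects who enter DOR and TTR. A subject lost from PR who later reaches CR would stay in those analyses, but with a late response date. Nothing in the SAP would detect or repair this.

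**Working it through.** The plan states no ORR figure to reproduce, so the check is to run cases through the criteria as written.

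**1. LPL/WM.** The rules as coded, with a fall meaning a percentage decrease from baseline:
- VGPR: fall above 90 and the other CR criteria met.
- PR: fall at least 50 and SPD decrease above 0.
- MR: fall from 25 to below 50 and no SPD increase.

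The exception in the opening line of the PR list does not change this. Whether the two WM items replace the general items or add to them, an SPD decrease is needed.

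| IgM fall | SPD absent or unchanged | Any SPD decrease |
|---|---|---|
| 30%, 49% | MR (in ORR) | MR (in ORR) |
| 50%, 60%, 80%, 90% | none of CR, VGPR, PR, MR | PR (in ORR) |
| 95% | VGPR if the other CR criteria are met, otherwise none | at least PR |

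A 40% fall lies in the first band and a 70% fall in the second. The SD text does not accept the second band either, because the IgM fall is large enough for PR. Above 90%, the other CR criteria include a negative marrow, and node-free subjects are eligible precisely because their marrow is involved.

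Best overall response is the best category recorded before progression (6.20.7.1). A subject already recorded as MR at an earlier visit therefore stays in ORR, though tabulated as MR rather than PR. The loss from ORR falls on subjects never recorded as MR, for example those whose IgM is already down by 50% or more at the first assessment.

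**2. PET.** Take a 70% SPD decrease, a residual enlarged node, no new or worsening disease, and a pretreatment PET that was positive. The marrow item is read as conditional.
- On-treatment PET positive: PR.
- On-treatment PET negative: not CR (node size) and not PR (PET clause).
- No on-treatment PET: PR.

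The negative-PET result is the same if the marrow item is read as a strict requirement.

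**3. Marrow item.** With masses gone:
- Marrow negative: CR.
- Marrow positive, no PET: PR.

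With a 70% SPD decrease, a residual mass, no PET, and marrow negative or not sampled, the result is PR when the item is read as conditional.

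**4. Size.** Each reclassified subject moves ORR by 1/n:
- 1/40 = 2.5 points (MCL, DLBCL or FL at full size).
- 1/45 = 2.2 points (other iNHL at full size).

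As an assumed example, 9/45 = 20.0% (exact 95% CI 9.6 to 34.6). Restoring two subjects gives 11/45 = 24.4% (12.9 to 39.5).

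**5. Primary endpoint.** Exact recursion of the futility rule (Beta(0.5, 1.5) prior, looks from n=10 to 40) at true rates 0.1 to 0.5 gives 0.837, 0.319, 0.072, 0.012 and 0.0016. Protocol Table 8-3 states 0.8408, 0.3162, 0.0685, 0.0125 and 0.0015, so the table reproduces. It depends only on progression and death, not on the PR text.

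**The case against.** The strongest reply is that best response comes from the IRC, whose reading methods sit in a charter (Protocol 9.4) that is not among the documents. SAP 6.1.1 shows that the charter does carry operational progression rules, so it may already close both gaps. That stands, and it limits the conclusion to a risk.

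The LPL/WM contrast also rests on treating an absent SPD as meeting no increase while failing any decrease. Among subjects with lesions it arises only when SPD is exactly unchanged, since an increase defeats MR too. Both statements are correct. But Protocol 3.2 gives subjects without measurable disease their own assessment by marrow, IgM and cryoglobulin, so they are meant to be classifiable. A still more literal reader could cite 6.20.7.8, which makes missing images not evaluable. For unscanned subjects that would remove MR as well, which supports clarification.

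The PET gap is narrow. PET is unscheduled, and for variably avid or unknown-avidity disease with no pretreatment PET, or a negative one, the text already falls back on CT.

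A reader might also infer four stronger things that the documents do not support:
- **Subjects with cleared marrow are excluded from response.** The marrow item concerns a subject who would otherwise be CR. Masses gone with a negative marrow is CR, and Protocol 6.5 does not require marrow sampling when CR is not otherwise met. Forcing the item on everyone would remove every PR with a residual mass and make the 50% SPD rule redundant. The item is misplaced, not harmful.
- **VGPR requires the monoclonal protein to disappear.** The word other most naturally excludes the IgM item that the VGPR rule itself replaces.
- **ORR, DOR and TTR are wrong.** Without the charter or any counts this is not shown.
- **All NHL subjects are exposed.** Full enrolment of those cohorts (3 × 40 + 45 = 165) is not the number meeting either gap.

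**Conclusion.** The point holds in limited form. Read literally, Protocol 6.20.7 drops two groups from response: LPL/WM subjects with an IgM fall of at least 50% and an absent or unchanged SPD (above 90%, unless the other CR criteria are met), and subjects with at least 50% shrinkage, a residual enlarged node and a PET turned from positive to negative. The LPL/WM gap is the stronger, because the rule is non-monotone against MR in a subgroup that the protocol chose to enrol.

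The consequence is a possible understatement of ORR, and incomplete DOR and TTR populations, in the NHL cohorts. It assumes that the IRC applied the text as written. The number of subjects is not given, nor is the LPL/WM share of the 45, so only the per-subject shifts above can be stated. CLL response is defined separately in Protocol 6.21 and is unaffected, as is the primary PFS rate. This is a secondary-endpoint definition that should be corrected; it does not threaten the main conclusion.

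**What to change.** In Protocol 6.20.7:

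- For LPL/WM with absent or unchanged SPD, judge PR on an IgM fall of at least 50% with no new or worsening disease and no SPD increase, so that a deeper fall cannot lose responder status.
- State that a negative on-treatment PET does not remove PR when the 50% SPD criterion is met.
- Mark the persistent-marrow item as an alternative route to PR.
- Correct MRI to PET in the item on typically FDG-avid lymphoma.
- State that the other CR criteria required for VGPR leave out the IgM and monoclonal-protein item.

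Apply the same rules in the SAP derivation of best overall response, record them in SAP 6.3, and confirm that the IRC charter matches.

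The study is open-label and the MM-formulation cohorts, which include every NHL cohort, are closed to enrolment (Protocol Table 5-1). The rules should therefore be fixed before data finalization, applied to all subjects alike, and every changed best response reported with its category under both wordings. The cost is wording in three documents and re-derivation for probably a few subjects; no new data are needed.

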6.20.7.5. Minor Response (LPL/WM only)

To satisfy criteria for MR, the following criteria must be met:

A $\geq 25\%$ but $<50\%$ decrease from baseline in monoclonal IgM concentration by SPEP or total serum IgM quantitation by nephelometry

- No increase from baseline in the SPD of the index nodal and extra-nodal lesions (eg, splenic or hepatic nodules)
- No increase in the size of non-index nodes or non-measurable disease
- No increase in the size of the liver or spleen and no new organ enlargements

6.20.7.6. Stable Disease

To satisfy criteria for SD, all of the following criteria must be met:

- No evidence of new disease
- Neither sufficient tumor shrinkage from baseline to qualify for PR nor sufficient evidence of tumor growth from nadir to qualify for PD

- If the subject has LPL/WM, neither a sufficient decrease from baseline in either monoclonal IgM concentration or total serum IgM quantitation by nephelometry to qualify for MR or PR nor a sufficient increase from nadir in either monoclonal IgM concentration by SPEP or total serum quantitation by nephelometry to qualify for PD

6.20.7.7. Progressive Disease

The occurrence of any of the following events indicates PD:

- Evidence of any new disease that was not present as baseline:
 - A new node that measures > 1.5 cm in any diameter
 - A new node that measures > 1.0 cm to ≤ 1.5 cm in the LD and > 1.0 cm in the LPD
 - Unequivocal reappearance of an extra-nodal lesion that had resolved (ie, had previously been assigned a PPD of 0 cm^2)
 - A new unequivocal extra-nodal lesion of any size
 - New non-index disease (eg, effusions, ascites, or other organ abnormalities) of any size unequivocally attributable to lymphoma (usually requires PET, biopsy, cytology, or other non-radiologic confirmation to confirm disease attributable to lymphoma). Note: Isolated new effusions, ascites, or bone lesions are not sufficient evidence alone of PD unless histologically confirmed. In subjects with no prior history of pulmonary lymphoma, new lung nodules identified by CT are usually benign. Thus, a declaration of PD should not be made if this is the only manifestation of an apparently new lesion.
- Evidence of worsening of nodal or extra-nodal index lesions:
 - Increase from the nadir by $\geq 50\%$ in the SPD of index lesions
 - Increase from the nadir by $\geq 50\%$ in the LD if an individual node or extra-nodal mass that now has an LD > 1.5 cm and an LPD of > 1.0 cm.
- Unequivocal increase in the size of non-index lesions or non-measurable disease (eg, pleural effusions or bone lesions)
- An unequivocal increase in the size of the liver, spleen, or other organ
- If PET performed (eg, DLBCL):
 - The appearance of any new lesion compatible with lymphoma with confirmation by other radiographic or histological modalities.
 - The reappearance of any activity in a pre-existent lesion that meets size criteria for a new lesion on CT

- Pseudo-progression characterized by a paradoxical rise in serum IgM followed by a delayed response has been recognized early in the course of treatment of subjects with WM/LPL treated with chemotherapy and immunotherapy. The time to responses following pseudo-progression may be delayed for >4 months in some cases. Expert opinion specifically cautions against premature disease response assessment in LPL/Waldenström's therefore unless there is compelling clinical and objective data of progression all subjects should have at least 4 months of treatment before an assessment of PD is made. When assessing for progression a bone marrow biopsy and/or CT scan should be used in conjunction with serum IgM levels to assess disease burden. Criteria for progression based on serum IgM include, a $\geq 25\%$ increase from the nadir in either monoclonal IgM concentration by SPEP or total serum IgM quantitation by nephelometry (with confirmation by a repeat measurement) at least 6 weeks apart.
- An absolute increase of at least 0.5 gram/dL is required to define progression with confirmation at least 6 weeks apart.

Note: If there is uncertainty regarding whether there is true progression, the subject may continue study treatment and remain under close observation (eg, evaluated at 4-week intervals). If subsequent evaluations suggest that the subject is experiencing progression, then the date of progression should be the timepoint at which progression was first identified. A single PD determination followed by a determination that indicates either no change or improvement in disease prior to the single PD observation will not be considered PD.

